1.3 PREVIOUS HUMAN EXPERIENCE

In addition to the extensive clinical experience with HSA, Ampio Pharmaceuticals, Inc. has completed multiple clinical studies to evaluate the safety and treatment effect of Ampion in subjects with OAK. The study is summarized in Section 1.5.

1.4 PRECLINICAL DATA

1.4.1 Pharmacology Studies

In vitro pharmacology studies demonstrated that a low molecular weight fraction (< 3000 daltons [Da]) of more than five commercial preparations of HSA, and a cyclized dipeptide

contained in that fraction, Asp-Ala diketopiperazine (DA-DKP) have a range of anti-inflammatory properties, which may be expected to ameliorate the symptoms of inflammation, including pain, in man ([Bar-Or et al 2006](#)). These studies showed reduced inflammatory cytokine production from human T lymphocytes *in vitro* via modulation of signal transduction through increased expression of Rap-1, and inhibition of macrophage activation. In addition, DA-DKP enhanced integrity of human endothelial cell junctions in the transendothelial electrical resistance (TEER) assay, which would result in decreased vascular permeability to the influx of inflammatory cells *in vivo*. No pharmacokinetics studies were performed as the plasma levels of the constituents of the < 5000 Da preparation, including DA-DKP, after intra-articular injection of a therapeutic dose in man or in laboratory animals are anticipated to be below the limits of detection. For more information, consult the Investigator Brochure.

1.4.2 Toxicity and Safety Studies

HSA and other components of serum albumin preparations are species specific and may be expected to be immunogenic if repeatedly injected into non-human species, even at very low concentrations. For this reason, it was not possible to perform formal toxicological studies in animals.

1.5 CLINICAL EXPERIENCE

Ampio has conducted multiple clinical studies to evaluate the treatment effect and safety of Ampion in subjects with OAK. Ampion has been administered across 6 clinical studies as a single intra articular (IA) injection or as three IA injections administered every two weeks. 3 single-dose pivotal Phase 3 studies, 2 multi-dose studies, and 1 multiphase single-dose phase 1b study have been completed. An overview of the efficacy studies is provided in the [Table 1.5.1](#)

For the clinical development program, all studies were conducted in subjects with moderate to moderately severe pain due to OA of the knee. Subjects were required to have x-ray findings demonstrating KL grade 2, 3, or 4. All studies enrolled subjects with KL 4. In addition, eligible subjects had at least moderate pain at Baseline (defined as a score of at least 1.5 on the WOMAC Index 3.1, 5-point Likert pain subscale at screening) in the study knee, which was to have been symptomatic for greater than 6 months with a clinical diagnosis of OA confirmed by radiological evidence. The clinical effects of treatment on OA pain were evaluated during clinic visits, with phone call follow-ups at intermittent times.

Table 1.5.1
**Summary of the Studies Conducted with Ampion™ Administered as an Intra Articular
Injection to the Knee**

| Study | Phase | N | N, KL 2, 3, 4 | Route of Administration | Primary outcome | Primary endpoint | Additional outcomes | Test product |
|--|-------|-----|--------------------|---|---|---------------------|---|------------------------------|
| Single-Injection Phase 3 Studies in Support of Efficacy & Safety | | | | | | | | |
| AP-003- A | 3 | 329 | 115 / 139 / 75 | Single IA injection | WOMA C A pain, 5- point Likert scale | Week 12 | WOMAC B WOMAC C PGA OMERACT -OARSI Rescue analgesia | Ampion, 4- mL or 10ml* |
| AP-004 | 3 | 538 | 133 / 195/ 210 | Single IA injection | WOMA C A pain, 5- point Likert scale | Week 12 | WOMAC C PGA WOMAC A pain over 12 weeks | Ampion, 4- mL |
| AP-003- B | 3 | 480 | 101 / 247 / 132 | Single IA injection | WOMA C A pain, 5- point Likert scale | Week 12 | WOMAC B WOMAC C PGA Rescue analgesia WOMAC A pain with movement, pain at rest | Ampion, 4- mL |
| Additional Clinical Studies in Support of Safety | | | | | | | | |
| AP-007 | 1 / 2 | 47 | 2 / 23/ 15 | Multiple IA injection; 3 injections, every 2 weeks | WOMA C A pain, 5- point Likert scale | Week 20 | WOMAC B WOMAC C PGA Physical activity Radiologic changes | Ampion, 4-mL |

| | | | | | | | | |
|--------|-------|------|---------------|--|---|---------------------------|---|---|
| AP-008 | 3 | 342 | 0 / 114 / 228 | Multiple IA injection; 3 injections, every 2 weeks | WOMA C A pain, 5- point Likert scale | Week 20 | WOMAC B WOMAC C PGA Physical activity WOMAC A pain with movement | Ampion, 4-mL |
| AIK | 1 / 2 | 103 | 33 / 69 / 1 | Single IA injection | Pain, 10- point NRS | Day 3, 8, 30 and 84 | WOMAC total, parts A, B, C Range in motion Rescue analgesia | Ampion 10 ml, alone or in solution with betamethasone and/or lidocaine and/or saline |
| Total | | 1839 | | | | | | |

*Both doses of Ampion, 4-mL and 10 mL, are safe, efficacious and well tolerated. In the absence of a difference in efficacy for the 4-mL and 10 mL Ampion doses, the lower dose of 4-mL will be used for subsequent phase 3 studies.

[figure not shown]
In all three well-controlled, single-injection studies, Ampion demonstrated a numerically greater effect in the KL 4 subjects compared to saline, indicating a reproducible and consistent response. Analysis of the combined data demonstrate a statistically significant result in this underserved patient population. [Table 1.5.2](#) presents the data for KL 4 subjects from all single-injection studies, analyzed according to the SAP for the respective study.

Table 1.5.2
Descriptive Statistics and Analysis Results for KL 4 Subjects for Each Study and All Studies Combined

| Study ID | Parameter | Saline | Ampion | Unadjusted Diff. (Ampion-Saline) | LS Adjusted Diff. (Ampion-Saline) |
|-----------------|-----------|--------|--------|-------------------------------------|--------------------------------------|
| Combined | N | 223 | 194 | | |
| | Mean | -0.62 | -0.82 | -0.21 | -0.19 |
| | Std. Dev. | 0.883 | 0.817 | | |
| | p-value | | | 0.0125 | 0.0155 |
| AP-003-A | N | 43 | 32 | | |
| | Mean | -0.51 | -0.86 | -0.35 | -0.42 |
| | Std. Dev. | 0.906 | 0.772 | | |
| | p-value | | | 0.0774 | 0.0164 |
| AP-003-B | N | 67 | 65 | | |
| | Mean | -0.62 | -0.81 | -0.19 | -0.14 |
| | Std. Dev. | 0.926 | 0.842 | | |
| | p-value | | | 0.2197 | 0.3516 |
| AP-004 | N | 113 | 97 | | |
| | Mean | -0.65 | -0.82 | -0.17 | -0.15 |
| | Std. Dev. | 0.851 | 0.823 | | |
| | p-value | | | 0.1440 | 0.1765 |

[Figure 1](#) visually represents the consistent reduction in pain for Ampion-treated subjects over a 12-week period.

Figure 1.
LS Mean Change for Ampion-Treated Subjects Over Time and by Study

In accordance with FDA guidance on osteoarthritis, responder analysis according to the OMERACT-OARSI criteria was applied to previously conducted clinical trials, [Table 1.5.3](#).

Table 1.5.3

Responder analysis in KL 4 subjects across single injection studies using OMERACT-OARSI criteria

| Study ID | Ampion Responder (%) |
|----------|----------------------|
| AP-003-A | 59.4% |
| AP-003-B | 59.7% |
| AP-004 | 57.7% |
| Combined | 58.6% |

In addition to the efficacy analysis described in this section, Ampion has also demonstrated a robust safety profile across the three well-controlled, single-injection studies, as well as the multiple-injection and early phase trials ([Table 1.5.4](#)). No drug-related Serious Adverse Events (SAEs) have been reported in 1,839 subjects treated during the clinical development program. The Adverse Event (AE) profile is similar for Ampion and saline, with a majority of the AEs of minor or moderate severity and unrelated to treatment.

Table 1.5.4
Summary of Treatment-Emergent Adverse Events

| Treatment emergent AE | Saline | Ampion |
|---------------------------------|-----------|-----------|
| Overall | N=907 | N=932 |
| One or more TEAE | 425 (47%) | 421 (45%) |
| One or more related TEAE | 63 (7%) | 73 (8%) |
| KL grade 4 | N=338 | N=326 |

| | | |
|---------------------------------|-----------|-----------|
| One or more TEAE | 150 (44%) | 145 (44%) |
| One or more related TEAE | 20 (6%) | 24 (7%) |

Conclusions

Clinical efficacy observed in previous single-injection studies suggest that Ampion safely relieves pain due to severe, KL 4, osteoarthritis of the knee, the most severe form of OAK, for which there is no FDA approved treatment alternative. While opioids can treat pain, and total knee replacement can excise the affected tissues, the ability to treat OAK pain and inflammation locally is an unmet medical need. Currently, when KL 4 subjects are treated for OAK, they are receiving treatment using intra-articular therapy (such as viscosupplementation) that were not studied, nor required in their device approvals to demonstrate efficacy in the KL 4 population ([Rutjes 2012](#)). Without surgery, with only a single intra-articular injection of Ampion, KL 4 subjects are able to achieve clinically meaningful pain relief.

2 RATIONALE FOR THE STUDY

This study is designed to follow on from the 12-week AP-003-C main study. This is an open label extension (OLE) to evaluate the safety of repeated dosing of a 4-mL IA injection of Ampion™ every 12 weeks for a total of 52 weeks of study visits.

2.1 RATIONALE FOR THE DOSES AND THE DOSING REGIMEN

This trial will use the 4-mL volume of Ampion™ used in previous single-injection studies (AP-003-A, AP-004, AP-003-B, and AP-003-C).

3 STUDY DESIGN

3.1 STUDY DESIGN OVERVIEW

Subjects who have completed the AP-003-C main study (n=161) will be offered the option to roll-over to the open label extension study (AP-003-C-OLE) at their final visit of the AP-003-C main study (Visit 7). Enrollment into the AP-003-C-OLE study (Visit 9) allows a 170-day screening window from the AP-003-C main study Visit 7. AP-003-C-OLE study will include the following visits:

Visit 9/Enrollment (Day-170 to Day 0, but not to occur before completion of AP-003-C main study) in-office visit, Visit 10 (24 hours after enrollment post injection follow-up telephone call), Visit 11 in-office visit (Day 84 ±14 days), Visit 12 (24 hours after Visit 11 post injection follow-up telephone call), Visit 13 in-office visit (Day 168 ± 14 days), Visit 14 (24 hours after Visit 13 post injection follow-up telephone call), Visit 15 in-office visit (Day 252 ± 14 days), Visit 16 (24 hours after visit 15 post injection follow-up telephone call), Visit 17 final in-office visit (Day 280 ± 14 days).

The safety of repeat dosing will be evaluated at all visits; in-office visit safety assessments will include vital signs, physical exams, evaluation of AEs, and laboratory analysis. Phone visits will evaluate for AEs.

The clinical effects of treatment on OA pain will be evaluated during all in-clinic visits using the Western Ontario and McMaster Universities Arthritis Index (WOMAC®) osteoarthritis Index 3.1 and the Patient's Global Assessment of disease severity (PGA). The WOMAC will also be utilized to assess the contralateral knee pain at Enrollment/Visit 9 and Visit 17 (or Early Termination Visit).

The WOMAC® is a validated pain scoring system and sets the standard for the subject response. In order not to bias the collection of data, only questions from the validated WOMAC pain scale will be asked of subjects.

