3.2 STUDY OBJECTIVES

3.2.1 Primary Objective

The primary trial objective is to carry on from the AP-003-C main study (one injection) and evaluate the safety of a 4-mL intra-articular (IA) injection of Ampion™ with repeat dosing every 12 weeks for 52 weeks and/or with five total injections of Ampion™.

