5 STUDY PLAN AND PROCEDURES

Subjects will receive an IA injection of Ampion™ at Visit 9, Visit 11, Visit 13 and Visit 15 of AP-003-C-OLE. Telephone contact will be made with the subject 24 hours after each IA injection. The subject will be followed until Visit 17. Safety of repeat injections every 12 weeks for 36 weeks will be evaluated during every visit (in-clinic and telephone); in office-visits will evaluate vital signs, physical exam, adverse events, and blood tests (Visit 17 or Early Termination Visit 18 only). Clinical effects of treatment on OA pain will be evaluated during in-clinic visits at Visit 9, Visit 11, Visit 13, Visit 15 and Visit 17 using the WOMAC osteoarthritis Index 3.1 (pain subscore, stiffness subscore and function subscore) and an overall global severity assessment (Patient's Global Assessment [PGA]). The WOMAC will also be utilized to assess the contralateral knee pain at Visit 9 and Visit 17 (or Early Termination Visit).

The assessments and procedures performed at each subject visit or contact are described in Section 5.1 Description of Study Visits and in Table 6.1, Schedule of Assessments and Procedures.

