6.2 SAFETY PARAMETERS

Based on results of previous studies of a single intra-articular injection of Ampion™ < 5 kDa ultrafiltrate of 5% HSA in adults with OA of the knee in which no clinically significant differences between active and placebo were found, safety will be assessed by recording adverse events, vital signs, results of physical examination, by recording prior and concomitant medications, and safety labs (at the Visit 17/Early Termination visit only).

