9.3 RECORDING OF ADVERSE EVENTS AND SERIOUS ADVERSE EVENTS

Recording and reporting of adverse events should be in accordance with the FDA final “Guidance for Industry and Investigators Safety Reporting Requirements for INDs and BA/BE Studies” of December 2012.

Any AE is to be recorded in the eCRF. In order to avoid vague, ambiguous, or colloquial expressions, the AE should be recorded in standard medical terminology rather than the subject’s own words. Whenever possible, the investigator should combine signs and symptoms that constitute a single diagnosis.

The existence of an AE may be concluded from a spontaneous report of the subject; from the physical examination; or from special tests e.g., laboratory assessments, where applicable, or other study-specified tests (source of AE).

The reporting period begins from the time that the subject receives their first IA injection at the Baseline visit of the AP-003-C main study through subject’s Final Visit 17 at 40 weeks of AP-003-C-OLE study. Any events continuing at study exit will be followed for 30 days or to resolution, or until no improvement is expected, whichever comes first. Any SAE occurring after the reporting period must be promptly reported if a causal relationship to the investigational drug is suspected. If the subject begins a new therapy, the safety reporting period ends at the time the new treatment is started, however, death must always be reported when it occurs during the study period irrespective of intervening treatment.

Each AE is to be evaluated for duration, severity, seriousness, and causal relationship to the investigational drug. The action taken and the outcome must also be recorded.

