10.3.11 Data presentation

10.3.11.1 Demographic and Baseline Characteristics:

Demographic (e.g., age, sex, race, ethnicity) and baseline characteristics (e.g., weight, height) summarized using descriptive statistics, overall and by treatment group for the ITT analysis population.

10.3.11.2 Medical History and Physical Examination:

The number and percent of subjects with past and current medical disorders at the time of enrollment will be presented overall and by treatment group for the ITT analysis population. Results of any abnormalities documented from the physical examination will be summarized overall and by treatment group for the safety and ITT analysis populations.

10.3.11.3 Concomitant Medications or Treatments:

The number and percent of subjects receiving concomitant medications or treatments prior to and during the study and at the final visit will be tabulated and presented overall and by treatment group for the ITT analysis population. Concomitant medications/treatments will be summarized using descriptive statistics and will be presented by type of drug (WHO DRUG classification) overall and by treatment group for the safety and ITT analysis populations.

10.3.11.4 Safety data:

Safety data will be evaluated by changes in vital sign measurements and the frequency and severity of AEs. Concomitant medication will be recorded for safety.

Adverse events:

The Investigator is responsible for monitoring the safety of subjects who have enrolled in the study. All AEs considered to be possibly related to Ampion™ will be followed until the event resolves or stabilized without further change. Subjects will be followed for the occurrence of AEs until completion of the study at Visit 17 or until early termination from the study (if applicable).

Investigators are required to document all AEs occurring during the clinical trial, commencing with the first day of treatment and including the protocol-defined post-treatment follow-up period on the appropriate CRF pages.

The severity of AEs (mild, moderate, severe), relatedness (related, possibly related, unrelated) along with the duration, action taken, and outcome (e.g., study withdrawal) will also be recorded. In addition, events meeting the criteria of a Serious Adverse Event (SAE) must be reported to the Sponsor within 24 hours on the SAE reporting forms.

10.3.11.5 Efficacy data:

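### No minimum interval between the last injection (Visit 15) and the final safety visit (Visit 17): in-window follow-up after the last dose runs from about 1 to 56 days

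*Protocol*

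**What the plan says.** Protocol 3.1 schedules the last two clinic visits as "Visit 15 in-office visit (Day 252 ± 14 days") and "Visit 17 final in-office visit (Day 280 ± 14 days"), with one contact between them: "Visit 16 (24 hours after visit 15 post injection follow-up telephone call"). The footnotes to Table 6.1 define Day 0 as the first injection of the extension, so both windows share one anchor. Section 5 places the injections "at Visit 9, Visit 11, Visit 13 and Visit 15 of AP-003-C-OLE", which makes Visit 15 the last.

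The primary objective (3.2.1) is safety under "repeat dosing every 12 weeks for 52 weeks and/or with five total injections", and the primary endpoint is the incidence and severity of treatment-emergent adverse events.

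On the end of collection, protocol 10.3.11.4 says "Subjects will be followed for the occurrence of AEs until completion of the study at Visit 17 or until early termination". Section 9.3 has events still present at exit followed for up to 30 days and adds: "Any SAE occurring after the reporting period must be promptly reported if a causal relationship to the investigational drug is suspected". Section 6.2 lists "safety labs (at the Visit 17/Early Termination visit only"). The schedule in SAP section 10 also marks a laboratory draw at enrollment.

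SAP 5.2 defines end of study with the same Visit 17 window. SAP 4.7.4 gives two end points for adverse event follow-up: one sentence stops it 12 weeks after the first dose, and the next paragraph carries documentation to the end of the study.

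**The concern.** Two windows of ± 14 days around visits 28 days apart touch at Day 266. Neither document sets a minimum interval, so compliance with both windows does not secure any set period of observation after the last dose.

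The main study contributed one injection and the extension adds four. For subjects randomized to Ampion in the main study, Visit 15 is therefore the fifth injection, and the time from Visit 15 to Visit 17 is the only period in which they are observed after five. It is also the least protected interval in the schedule. After the Visit 9, 11 and 13 injections, the next clinic visit is at least 56 days away.

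Immediate and next-day reactions are recorded at Visit 15 and at the Visit 16 call, ongoing events are followed, and later serious events suspected to be related must be reported. What is lost after an early Visit 17 is any new non-serious event, and any new serious event not suspected to be related. The only scheduled laboratory draw after repeat dosing in subjects who complete would also fall very soon after the last injection.

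The 12-week sentence in SAP 4.7.4 adds to this. Taken literally, it ends adverse event follow-up before the last two injections are given.

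**Working it through.** The plan states no figure for follow-up after the last dose, so there is nothing of its own to reproduce.

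**Windows (protocol 3.1, Table 6.1)**
- Visit 15: 252 ± 14 = Day 238 to 266.
- Visit 17: 280 ± 14 = Day 266 to 294.
- Nominal gap: 280 − 252 = 28 days.
- Longest gap: 294 − 238 = 56 days.
- Shortest gap from the windows alone: 266 − 266 = 0. The Visit 16 call comes 24 hours after Visit 15, so the realistic minimum is about 1 day (for example Day 265 then Day 266).

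**Comparison with earlier injections**
- Visit 9 to Visit 11: 84 ± 14 = 70 to 98 days.
- Visit 11 to 13 and Visit 13 to 15: (154 − 98) to (182 − 70), and likewise for the next pair, = 56 to 112 days.

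**Share of subjects with short follow-up**

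Booking behaviour is not in the documents, so each row is an assumption. In whole days there are 29 × 29 = 841 date pairs; dropping the single same-day pair leaves 840. The correlated rows join uniform visit dates by a Gaussian copula (simulated).

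| Assumed booking pattern | Under 14 days | Under 21 days |
|---|---|---|
| Visit 17 moves fully with Visit 15 | 0% | 0% |
| Correlation 0.75 | 1.2% | 10.8% |
| Independent, triangular around the nominal day | 4.7% | 20.0% |
| Correlation 0.5 | 5.0% | 18.5% |
| Independent, uniform | 104/840 = 12.4% | 230/840 = 27.4% |

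The mean gap stays at about 28 days throughout.

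**Numbers of subjects**

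The denominator is subjects who receive the Visit 15 injection. Assume that all of a 15% dropout occurs before Visit 15.
- From 161 (protocol 10.3.7): 161 × 0.85 = 136.85, which the protocol takes as 136. 0.124 × 136 = 16.9, so 0 to about 17 subjects under 14 days.
- From 100 (SAP 2.4): 100 × 0.85 = 85. 0.124 × 85 = 10.5, so 0 to about 11 subjects.

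**SAP 4.7.4 cut-off**

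Twelve weeks after the first extension dose is Day 84. Visit 13 is Day 154 to 182 and Visit 15 is Day 238 to 266, so both injections fall after it. Counting from the main-study dose would make the cut-off earlier still.

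**Feasibility of a 21-day minimum**
- Earliest permitted Visit 17 = the later of Day 266 and (Visit 15 + 21).
- Latest case: 266 + 21 = Day 287, before Day 294.
- Resulting gap: 21 to 56 days. The final visit stays within Day 266 to 294.
- Bookable days for Visit 17: 29 if Visit 15 is on or before Day 245; 294 − 273 + 1 = 22 if on Day 252; 294 − 287 + 1 = 8 if on Day 266.

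**The case against.** The strongest reply is that the primary endpoint covers the whole study, and total observation in the extension is Day 266 to 294 whatever the Visit 15 date. Under the least favourable booking pattern above, raising every gap below 21 days to 21 would add 1,750/840 = 2.1 days per subject, about 0.7% of 280 days. That is right, and it is why no bias in overall incidence is claimed. It does not answer the narrower point that the segment after the final dose has no floor.

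Other points stand in part:
- The 1-day gap is a corner case, and the count of 17 needs independent, uniform dates.
- The missed-visit rule (protocol 5.1.12) can be read as requiring a late Visit 15 by Day 265. The uniform figures then become 91/812 = 11.2% and 210/812 = 25.9%. The range of 1 to 56 days does not change.
- Subjects given saline in the main study receive four Ampion injections, not five. With 6:1 randomization, 6/7 of 136 is about 117, and the upper count falls to about 14. The objective is also worded as and/or.
- The documents do not single out 21 days. It is a judgement. A 28-day minimum would leave one bookable day after a Day 266 injection (266 + 28 = 294), and a 14-day minimum secures less.
- The SAP 4.7.4 sentence is a separate drafting conflict, and the protocol points clearly to Visit 17. It still needs correcting, because it concerns collection of the primary endpoint.

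**Conclusion.** The concern holds and should be fixed. In-window follow-up after the last injection runs from about 1 to 56 days with a nominal 28, and this rests only on the stated windows and the 24-hour call. How many subjects would be affected is uncertain: 0% to 12.4% under 14 days and 0% to 27.4% under 21 days, depending on assumed booking behaviour, or 0 to about 17 of 136 under 14 days with all dropout before Visit 15. The consequence is uneven capture of new events after the final dose and no assured safety period there. It is not a shift in mean follow-up and does not undermine the study as a whole. The 12-week cut-off in SAP 4.7.4 is wrong as written.

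**What to change.** - **Protocol.** Keep Day 280 ± 14 and require Visit 17 to be at least 21 days after the actual Visit 15 injection. One sentence in 5.1.9 and a footnote to Table 6.1 are enough; the window text repeated elsewhere can stand.
- **SAP.** Put the same rule in the end-of-study definition (5.2). Replace the 12-week sentence in 4.7.4 with collection to Visit 17 or early termination. Add a table of days from last injection to last adverse event contact.

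The cost is a written amendment with sponsor, IRB/IEC and Health Authority approval (protocol 11.3), a SAP update and one table from dates already recorded. No visit or procedure is added. The booking range for Visit 17 narrows after a late Visit 15, to 8 days at worst. If an amendment is impractical, the SAP correction and the table are still worth making alone, since the table would show any short follow-up.

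Anchoring Visit 17 at 28 ± 7 days after the last injection is a weaker alternative. It gives 21 to 35 days, but moves the final visit to Day 259 (238 + 21) through Day 301 (266 + 35). That is a 42-day spread instead of 28, with some final visits 7 days earlier than now.
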